9.3.3 Covariates

Logistic regression model was used to estimate propensity scores based on all covariates listed below:

- ✓ Age
- ✓ Gender
- ✓ Speciality of prescribers of OAC
- ✓ Time from AF diagnosis to initiation of OAC
- ✓ History of stroke or transient ischemic attack yes/no
- ✓ History of myocardial infarction yes/no
- ✓ History of coronary artery disease yes/no
- ✓ History of heart failure yes/no
- ✓ History of diabetes mellitus yes/no
- ✓ History of dyslipidemia yes/no
- ✓ History of arterial hypertension yes/no
- ✓ History of peripheral artery disease yes/no

- ✓ History of peptic ulcer disease yes/no
- ✓ History of dementia yes/no
- ✓ History of malignant lymphoma yes/no
- ✓ History of leukemia yes/no
- ✓ History of solid tumor cancer yes/no
- ✓ History of kidney impairment yes/no
- ✓ History of liver disease yes/no
- ✓ History of valvular disease yes/no
- ✓ History of bleeding (gastro-intestinal, etc.) yes/no
- ✓ History of hospitalization yes/no
- ✓ CHA₂DS₂-VASC
- ✓ HAS-BLED Score
- ✓ Year of Initiating Treatment
 - Index date falling within 12 months starting from 14th of March in 2011 and then from 1st of March of each respective year in 2012 to 2016, then to 30 June 2016.
- ✓ Concomitant medication (prescription claims within the baseline period)
 - yes/no for the following:
 - ◊ aspirin
 - ◊ ticlodipine
 - ◊ cilostazole
 - ◊ clopidogrel
 - ◊ angiotensin receptor blockers or angiotensin converting enzyme inhibitors
 - ◊ beta-blocker
 - ◊ amiodarone
 - ◊ procainamide
 - ◊ disopyramide
 - ◊ flecainamide
 - ◊ pilcicainide
 - ◊ procainamide
 - ◊ calcium-channel blocker
 - ◊ digoxin
 - ◊ diuretics
 - ◊ statins
 - ◊ proton-pump inhibitor
 - ◊ H₂ receptor antagonist

The disease, condition/disease for AF risk score calculation, AF risk score, and concomitant medication are defined as [Table 4](#), [Table 5](#), [Table 6](#), [Table 7](#), [Table 8](#).

Table 4

Definition of clinical history

| Disease | Definition | |
|-------------------------------------|---|---|
| | ICD10code | prescription |
| Stroke or transient ischemic attack | I60-I64, G45 | - |
| Myocardial infarction | I21-I23 | - |
| Coronary artery disease | I251 | - |
| Heart failure | I110, I130, I132, I420, I50 | Prescribed furosemide (defined by generic name) |
| Diabetes mellitus | E100, E101, E109, E110, E111, E119, E14 | Prescribed drugs used in diabetes (defined by ATC code as A10) |
| Dyslipidemia | E78 | - |

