| Arterial hypertension | I10-I15 | Prescribed 2 or more types of anti-hypertensive (defined in Table 2b) |
| Peripheral artery disease | I702-I709, I71, I739 | - |
| Peptic ulcer disease | K22, K25-K28 | - |
| Dementia | F00-F03, G30 | - |
| Malignant lymphoma | C81-C88 | - |
| Leukemia | C90-C96 | - |
| Solid tumor cancer | C00-C80, C97 | - |
| Kidney impairment | N28 | - |
| Liver disease | K70-K77 | - |
| Valvular disease | I059, I089, I358, I38, I48 | - |
| Bleeding (gastro-intestinal, etc.) | K25-K29, K922 | - |

Table 5 Definition of anti-hypertensive

| Class/type | ATC code |
|--|---|
| Calcium channel blockers (CCB) | C08A0 |
| Angiotensin receptor blockers (ARB) | C09C0 |
| Angiotensin converting enzyme inhibitors (ACE) | C09A0 |
| Diuretics | C03A1, C03A2, C03A3, C03A7, C03A9 |
| Thiazide diuretic | C03A3 (Thiazide, plane), C02D0 (Rauvolfia alkaloids) |
| Beta blocker | C07A0 |
| Alpha-adrenoreceptor antagonists | C02A2 |
| Potassium-sparing agents | C03A1 |
| Others | C02A1 (Antihypertensives), C02A3 (Antihypertensives for pulmonary arterial hypertension), C09X0 (Other agents acting on the renin-angiotensin system) |
| Combination agents | C09D1 (ARB and diuretics), C09D3 (ARB and CCB) |

Table 6

Definition of condition/disease for AF risk score calculation

| Condition/disease | Definition | |
|---|---|--|
| | ICD10code | prescription |
| Congestive heart failure or left ventricular dysfunction | I110, I130, I132, I420, I50 | Prescribed furosemide (defined by generic name) |
| Stroke (ischemic stroke, transient ischemic disease, or systemic embolism) | I63, I64, G45, I74 | |
| Vascular disease (myocardial infarction, peripheral arterial disease, or aortic plaque) | I21-I23, I702-I709, I71, I739, I700 | |
| Abnormal renal function | I12, I13, N00-N05, N07, N11, N14, N17-N19, Q61 | |
| Abnormal hepatic function | B150, B160, B162, B190, K704, K72, K766, I85 | |
| Stroke (ischemic stroke or transient ischemic attack) | I63, I64, G45 | |
| Bleeding | I60, I61, I62, D62, J942, H113, H356, H431, N02, N95, R04, R31, R58, K250, K260, K270, K280, K290, S063, S064, S065, S066 | Aspirin and clopidogrel: defined by general name |
| Drugs (aspirin, clopidogrel, or non-steroidal anti-inflammatory drugs) | | Non-steroidal anti-inflammatory drugs defined by ATC code (EPHMRA) as M01A |
| Alcohol intake | F10, G312, G621, G721, I426, K292, K70, K860, L278, O354, T51, Z714, Z721 | |

Table 7

AF risk score calculation

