| Risk score | Disease/condition | Points if present |
|--|---|-------------------|
| CHADS ₂ (9) | Congestive heart failure or left ventricular dysfunction | 1 |
| | Hypertension | 1 |
| | Age \geq 75 years | 1 |
| | Diabetes mellitus | 1 |
| | Stroke (ischemic stroke, transient ischemic disease, or systemic embolism) | 2 |
| CHA ₂ DS ₂ VASc (10) | Congestive heart failure or left ventricular dysfunction | 1 |
| | Hypertension | 1 |
| | Age \geq 65 years | 1 |
| | Age \geq 75 years | 1 |
| | Diabetes mellitus | 1 |
| | Stroke (ischemic stroke, transient ischemic disease, or systemic embolism) | 2 |
| | Vascular disease (myocardial infarction, peripheral arterial disease, or aortic plaque) | 1 |
| | Female | 1 |
| HAS-BLED (10) | Hypertension | 1 |
| | Abnormal renal function | 1 |
| | Abnormal hepatic function | 1 |
| | Stroke (ischemic stroke or transient ischemic attack) | 1 |
| | Bleeding | 1 |
| | Labile international normalized ratio* | 1 |
| | Elderly Age (\geq 65 years) | 1 |
| | Drugs (aspirin, clopidogrel, or non-steroidal anti-inflammatory drugs) | 1 |
| | Alcohol intake | 1 |

*Not included due to unavailable information

Table 8

Definition of concomitant medication

| Drug | Definition | |
|------------------------------------|-----------------------------------|---|
| | ATC code | Generic name |
| Aspirin | - | Aspirin, aspirin dihydroxyaluminum aminoacetate magnesium carbonate |
| Ticlodipine | - | Ticlopidine hydrochloride |
| Cilostazole | - | Cilostazole |
| Clopidogrel | - | Clopidogrel sulfate |
| ARB or ACE | C09A0, C09C0, C09D1 | - |
| Beta blocker | C07A0 | - |
| Amiodarone | - | Amiodarone hydrochloride |
| Procainamide | - | Procainamide hydrochloride |
| Disopyramide | - | Disopyramide, disopyramide phosphate |
| Flecainide | - | Flecainide hydrochloride |
| Pilsicainide | - | Pilsicainide hydrochloride |
| CCB | C08A0 | - |
| Digoxin | - | Digoxin, metildigoxin |
| Diuretics | C03A1, C03A2, C03A3, C03A7, C03A9 | - |
| Statins | C10A1 | - |
| Proton pump inhibitor | A02B2 | - |
| H ₂ receptor antagonist | A02B1 | - |

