9.9 LIMITATIONS OF THE RESEARCH METHODS

- Unobservable factors or factors not captured in the database such as laboratory data not equally distributed in the treatment groups that may also influence the outcomes could lead to unobserved confounding.
- The anticipated sample size might be limited which might lead to imprecise results. Therefore the study can only be considered to be exploratory. Based on the expected small sample size there is also the risk of pure chance findings. No hypothesis testing is planned,
- All information of each patient is from consent giving DPC hospitals. If patients have visits to other non-DPC medical institutions, these data are not included in the MDV data.

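### Table 4 counts all of E14 as diabetes but only three subcodes each of E10 and E11, so some diabetic patients can be scored non-diabetic

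*Combined protocol and SAP*

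**What the plan says.** Section 9.3.3 puts diabetes into the propensity model as a binary term, "History of diabetes mellitus yes/no". Table 4 defines it in two columns. The ICD-10 column reads "E100, E101, E109, E110, E111, E119, E14". The prescription column reads "Prescribed drugs used in diabetes (defined by ATC code as A10").

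The rule for joining the two columns is not stated. Heart failure and arterial hypertension also have an entry in both columns, and the rule is missing there too.

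Diabetes also enters the model a second way. Table 7 gives it one point ("Diabetes mellitus | 1") in CHADS2 and in CHA2DS2-VASc, and CHA2DS2-VASc is itself on the covariate list. Table 6, headed "Definition of condition/disease for AF risk score calculation", has no diabetes row, so Table 4 holds the only definition of diabetes in the document.

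**The concern.** The code list is not consistent with itself. It takes one diabetes category whole and keeps only part of two others, with no explanation. Elsewhere in the same table a three-character entry covers a full category, as in "Dyslipidemia | E78". A patient's diabetes status can therefore turn on which category the coder chose, not on whether the patient has diabetes.

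What is at stake is confounding control. Sections 9.1 and 9.12 rely on new-user selection and propensity matching to deal with channelling and baseline risk. Section 9.7.1 plans a Cox model with treatment only, because no residual imbalance was found after matching. Nothing later in the analysis corrects a covariate that was built wrongly. A balance table on that covariate shows balance in the recorded variable, not in true diabetes status.

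**Working it through.** The plan states no figure that depends on this point, so the check is a comparison of the entries.

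**Assumptions.** A three-character entry means the whole category, and fourth characters run from .0 to .9.

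**Step 1: what the list keeps (Table 4).**

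| Category | Listed | Not listed |
|---|---|---|
| E10 | .0, .1, .9 (3 of 10) | .2 to .8 (7) |
| E11 | .0, .1, .9 (3 of 10) | .2 to .8 (7) |
| E14 | whole category | none |
| E12, E13 | not mentioned | all |

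Positions omitted within E10 and E11: 7 + 7 = 14. Each has a counterpart under E14 that counts.

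**Step 2: how a patient is scored under each join rule.** 1 means diabetic, 0 means non-diabetic.

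| Diabetes codes recorded | A10 drug recorded | AND | OR |
|---|---|---|---|
| Only omitted E10/E11 codes | yes | 0 | 1 |
| Only omitted E10/E11 codes | no | 0 | 0 |
| At least one listed code | yes | 1 | 1 |
| At least one listed code | no | 0 | 1 |

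Patients in the first two rows are always scored 0 under AND. Under OR they are scored 0 only if no A10 drug is recorded. The misclassification is therefore possible under both rules.

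**Step 3: which zeros the code list causes.** Put E10 and E11 in whole. Under AND, row 1 changes from 0 to 1, but row 2 stays 0 because no drug is recorded. Under OR, row 2 changes from 0 to 1, and row 1 was already 1. The truncation thus harms drug-treated patients under AND, and patients with no recorded A10 drug under OR.

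**Step 4: why a patient may have no recorded A10 drug.** The patient may be untreated, or treated elsewhere. Section 9.9 says: "If patients have visits to other non-DPC medical institutions, these data are not included in the MDV data". Section 9.11 adds that the database receives claims from about 12% of DPC hospitals.

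**Step 5: consequence per affected patient.** The diabetes covariate is 0 instead of 1. If Table 4 also feeds the scores, CHA2DS2-VASc is one point too low. Both errors go into the same model, since section 9.3.3 says: "Logistic regression model was used to estimate propensity scores based on all covariates listed below".

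**The case against.** The strongest reply is that few patients are likely to be affected. Anyone who also carries E109, E119 or any E14 code meets the code criterion, and under OR any recorded A10 drug is enough. This stands. It limits the point to patients whose only diabetes codes are the omitted ones.

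The propensity model also holds kidney impairment, peripheral artery disease, coronary disease, myocardial infarction, hypertension, hospitalization, statins and HAS-BLED. These may carry part of the same risk. This stands too, and it is a reason to expect a small effect.

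Care outside the database is a disclosed limitation that touches every covariate. That is fair, and a longer list cannot recover codes recorded elsewhere. It would, however, recover a patient whose omitted code is in the database and whose drugs are not.

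Section 9.7.1 refers to the 1160.279 protocol for matching detail, and that protocol may state the join rule. It is not available here. Table 4 in this protocol should be complete on its own.

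A reader might go further in two ways. One is to infer that, under AND, all treated patients with diabetic complications are missed. Table 4 does not support that, because E14 is whole and any additional listed code restores the patient. The other is to infer that matching leaves these patients unbalanced, or that the hazard ratio is biased in a known direction. That would need true diabetes status to differ between the matched groups, and nothing in the documents shows this. Nor do the documents describe the omitted subcodes or give stroke or bleeding risks for them, so no claim about sicker patients is made here.

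**Conclusion.** The point holds in a limited form. Table 4 can score a patient as non-diabetic when the only recorded diabetes codes lie in E10.2-E10.8 or E11.2-E11.8. Under AND this always happens; under OR it happens when no A10 drug is recorded. The error reaches the diabetes covariate directly. It reaches CHA2DS2-VASc only on the reading that Table 4 supplies the score's diabetes item, which is likely because no other definition exists, but is not stated.

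Matching may therefore fail to balance true diabetes status, and the planned balance assessment could not reveal it. The number of patients, the size of any effect on the hazard ratio and its direction cannot be derived from the documents. My judgement is that the effect is small, and smaller under OR than under AND if most coded patients have a recorded A10 drug. This is a minor correction to a covariate definition and does not undermine the design.

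**What to change.** - List E10 and E11 in Table 4 as whole categories, consistent with E14, or justify the restriction. State whether E12 and E13 are intended.
- State the AND/OR rule for each Table 4 row with a prescription entry: heart failure, diabetes and arterial hypertension. For diabetes, use a code OR an A10 prescription.
- Apply this one diabetes definition to the covariate and to the risk scores, and say so in Table 6.

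The edit itself is short. The cost is a re-run of the propensity model, the matching and the balance check. The matched sample may shift slightly from the feasibility figure of 4,427 per group in section 9.5. The statement in section 9.7.1 that no residual imbalance remained would need to be confirmed on the new match.

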Several real world evidence studies have been published recently to compare effectiveness and safety of dabigatran, rivaroxaban and apixaban using claims database from the U.S., Danish and Taiwan national claims databases.²⁻⁵ In addition, several validation studies have been reported using DPC hospital claims database. Yamaguchi et al assessed the positive predictive value (PPV) of MDV claims defined event definitions for deep vein thrombosis, pulmonary embolism and bleeding events against clinical diagnosis of a panel of experts who examined claims codes and reached a consensus.⁶ Although sample of events were relatively small (50 for each event) PPV for thromboembolic events was 75% and bleeding events was 73.3%. Yamana et al evaluated the DPC data identified Charlson co-morbid conditions from 4 mid-size acute care hospitals against chart review diagnosis for the validity of claims defined diagnosis.⁷ Specificity was found to be over 96%, although sensitivity was below 50%. PPV for cerebrovascular disease diagnosis was reported to be 86.4% with negative predictive value of 93.5%. Koretsune et al conducted a validation study on MDV database to calculate the PPV for stroke, systemic embolism (SE) and intracranial hemorrhage (ICH) utilizing methodology similar to that reported by Yamaguchi et al, and found the PPV of stroke, SE events (SEE) and ICH to be 74%, 26.7% and 85.0%.⁸ Second evaluation of SEE after changing claims definition increased the PPV to 86.7%.

There has been no comparative effectiveness or safety analysis of dabigatran vs. warfarin has been published using large scale Japanese claims database thus far.

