9.2 SETTING

MDV clinical database is used.

Definition

1. Index date: the date of first oral anticoagulant prescription, namely warfarin or dabigatran
2. Baseline period: 12 months prior to and including the index date
3. Drug exposure period: period of time from index date to the end of drug treatment determined by having continuous record of prescription with less than 14 days of gap in prescription (grace period) or by switching to another OAC (end of index treatment is then considered to occur the day before the prescription of the new OAC)
4. Follow-up period: the day after index date to the earliest of treatment discontinuation, day before switch, end of continuous enrolment in the database, end of study period or death.

Inclusion criteria

1. >18 year-old with confirmed diagnosis of non-valvular atrial fibrillation (NVAF, ICD 10 code I48)
2. New starters of dabigatran or warfarin

Proprietary confidential information © 2017 Boehringer Ingelheim International GmbH or one or more of its affiliated companies

3. No prescription of other OACs for 12 months prior to the index date, defined as the first prescription of OACs (the period is defined as baseline period)
4. Has an index date between 14th of March 2011 to 30 June 2016

Exclusion criteria

1. Having less than 12 months of enrolment prior to the index date
2. Dialysis or kidney transplant recipients in baseline period
3. Having atrial flutter, valvular AF, mechanical valve placement, rheumatic AF, mitral valve prolapse/regurge/stenosis in baseline period
4. Having record of deep vein thrombosis or pulmonary embolism <6 months before AF diagnosis in baseline period

The symptoms, diseases, or treatments in these criteria are defined by ICD-10 code, disease name, or medical care activity name (see Table 1).

Table 1

Definition of symptoms/diseases/treatment for inclusion/exclusion criteria

| Symptoms/diseases/treatment | Definition | | |
|-----------------------------|------------|----------------|--|
| | ICD10 code | Disease name | Medical care activity name |
| Dialysis | - | - | Including “dialysis” |
| Kidney transplant | T861, Z940 | - | - |
| Atrial flutter | - | Atrial flutter | - |
| Valvular AF | - | Valvular AF | - |
| Mechanical valve placement | T820 | - | Including “mechanical valve placement” |
| Rheumatic AF | I05-I09 | - | - |
| Mitral valve prolapse | I340 | - | - |
| Mitral valve regurge | I341 | - | - |
| Mitral valve stenosis | I050, I342 | - | - |

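### The valvular disease covariate in Table 4 includes the inclusion code I48 and so carries almost no valve information; kidney impairment (N28) shares no code with the renal list in Table 6, so renal control is indirect

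*Combined protocol and SAP*

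**What the plan says.** Inclusion criterion 1 in section 9.2 requires a "confirmed diagnosis of non-valvular atrial fibrillation (NVAF, ICD 10 code I48"). The look-back is defined there as "Baseline period: 12 months prior to and including the index date". Table 1 lists "Rheumatic AF | I05-I09" among the exclusions, with further mitral and mechanical-valve codes. The only renal exclusion is "Dialysis or kidney transplant recipients in baseline period".

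Section 9.3.3 makes valvular disease and kidney impairment yes/no covariates in the logistic propensity model. Table 4 gives the valve codes as "Valvular disease | I059, I089, I358, I38, I48" and defines kidney impairment by N28 alone. Table 6 defines abnormal renal function by I12, I13, N00-N05, N07, N11, N14, N17-N19 and Q61, and Table 7 turns that list into one HAS-BLED point. Two other Table 4 rows overlap the renal list: "Arterial hypertension | I10-I15" and "Heart failure | I110, I130, I132, I420, I50".

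Section 9.7.1 drops covariates seen in fewer than 10 patients, and drops CHADS2 for collinearity. Everything else stays in the model. The Cox model contains treatment only, on the ground that matching left no imbalance. That statement is referenced to a 1160.276 report, although the feasibility study is otherwise numbered 1160.279.

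**The concern.** A covariate that is yes for almost every patient cannot help to match on valve disease. It will also look balanced whatever the true distribution of valve codes. The elimination rule catches rare covariates, not near-universal ones.

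The renal point is one of incompleteness, not contradiction. Most coded renal disease enters the score only inside a summed total. A patient whose HAS-BLED point is renal can be matched to one whose point comes from NSAID use or alcohol, so matching on the total does not guarantee balance on its renal part.

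Within the restricted new-user cohort, matching is the only confounder adjustment, for both stroke/SE and major bleeding. If balance was judged on the Table 4 definitions, the finding that justified an unadjusted Cox model says nothing about I358/I38 or about the Table 6 renal codes.

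**Working it through.** The plan states no figure on this point, so there is none to reproduce. The check has a code comparison and a size estimate.

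**1. Valve codes.** The Table 4 list is {I059, I089, I358, I38, I48}.
- Overlap with the inclusion code: {I48}.
- Overlap with the Table 1 exclusions I05-I09: {I059, I089}.
- Left to discriminate: {I358, I38}.

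Let f be the share of patients with I48 in the look-back and v the share with I358 or I38. The documents give neither. Taking them as independent, flag prevalence is p = f + (1−f)v, and the correlation of the flag with a true valve code is v(1−p)/√[p(1−p)v(1−v)].
- f = 1: p = 1, variance 0, no contribution to the score.
- f = 0.99, v = 0.02: p = 0.9902, correlation 0.014.
- f = 0.90, v = 0.10: p = 0.91, correlation 0.009/0.0859 = 0.105.

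The flag is therefore near-constant even if up to 10% of patients lack I48 in the window.

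**2. Renal codes.** N28 and the Table 6 list have no code in common. Across all of Table 4, only I12 and I13 (under hypertension) and I130 and I132 (under heart failure) come from the Table 6 renal list. N00-N05, N07, N11, N14, N17-N19 and Q61 reach the score only through HAS-BLED.

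**3. Size of the renal gap (simulation; all inputs assumed).**
- 20,000 patients and 40 replicates in each of nine cells: renal prevalence 10, 15 or 20% (rising with age, hypertension and heart failure), crossed with an odds ratio for receiving dabigatran of 0.4, 0.5 or 0.6.
- Score covariates: age, hypertension, heart failure, diabetes, stroke, aspirin, clopidogrel, N28 (2%, independent) and the HAS-BLED total. 10% of coded renal patients also set the hypertension flag and 3% the heart failure flag.
- Matching as in section 9.7.1: 1:1 nearest neighbour, caliper 0.10 SD of the logit.
- Coding is either perfect or 50% sensitive and 98% specific. The second case is prompted by section 7, which reports for DPC-coded comorbidities: "Specificity was found to be over 96%, although sensitivity was below 50" per cent.

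Bias factor on the hazard ratio = [1 + p_d(RR−1)] / [1 + p_w(RR−1)], where p_d and p_w are the post-match true renal shares on dabigatran and warfarin. Largest cell, perfect coding: at RR 1.5, 1.0475/1.083 = 0.967; at RR 2.0, 1.095/1.166 = 0.939. Its standardised difference is 0.071/√[(0.095×0.905 + 0.166×0.834)/2] = 0.071/0.335 = 0.21.

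| Coding and cell | As written: p_d vs p_w | Factor at RR 1.5 / 2.0 | With direct renal flag | Factor at RR 1.5 / 2.0 |
|---|---|---|---|---|
| Perfect, mildest | 6.2% vs 9.0% | 0.987 / 0.975 | balanced | 0.998–1.000 |
| Perfect, largest | 9.5% vs 16.6% | 0.967 / 0.939 | balanced | 0.998–1.000 |
| 50%/98%, mildest | 6.2% vs 9.6% | 0.984 / 0.969 | 6.2% vs 8.7% | 0.988 / 0.977 |
| 50%/98%, largest | 9.5% vs 19.2% | 0.956 / 0.918 | 9.5% vs 16.6% | 0.967 / 0.939 |

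Shares are rounded, so a recalculated factor can differ by 0.001.

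Post-match renal standardised differences:
- Perfect coding: 0.10–0.21 as written, at most 0.007 with the flag.
- Imperfect coding, true renal disease: 0.13–0.28 as written, still 0.10–0.21 with the flag, although the coded variable itself balances (0.06–0.13 falls to at most 0.004).

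Under imperfect coding the flag removes about 26–30% of the log bias. In the largest cell at RR 2.0: 1 − ln(0.939)/ln(0.918) = 1 − 0.0629/0.0856 = 0.26.

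**4. Comparison with random error.** Using N = 4,421 per group and 0.40487 years of follow-up (Table 9), a rate of 0.03 per year and HR 0.716 (section 9.5):
- Warfarin events: 4421 × (1 − exp(−0.03 × 0.40487)) = 53.4.
- Dabigatran events: 4421 × (1 − exp(−0.03 × 0.716 × 0.40487)) = 38.3.
- Total 91.7; SE(log HR) = √(1/53.4 + 1/38.3) = 0.212; 95% CI factor exp(1.96 × 0.212) = 1.51.

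The largest renal bias, |ln 0.918| = 0.0856, is about 0.4 of one standard error.

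**The case against.** The two parts are unequal. The I48 entry is an error on the page, but a constant flag drops out of a logistic model without harm, and the exclusions already remove mitral, rheumatic and mechanical-valve disease. The kidney row contradicts nothing: a history covariate and a published risk score may use different lists, and renal disease does enter through N28, HAS-BLED, I12/I13 and the dialysis/transplant exclusion. Section 9.7.1 says the covariates were evaluated in 1160.279, the Abstract already plans a description of patients before and after matching, and the study is declared exploratory.

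The renal figures also rest wholly on assumptions. The simulation leaves out listed covariates such as liver disease, bleeding history, diuretics, ARB/ACE inhibitors and hospitalization, and its result depends on how common the other HAS-BLED components are.

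Much of this stands. Near-constant is the right description, because no look-back is stated for the Table 4 diagnoses. The valve effect is probably small, and the upper end of the renal range may be overstated. With other assumed comorbidity rates and the omitted covariates added, the largest-cell standardised difference fell from 0.185 to 0.154 (NSAID use 10%) or from 0.213 to 0.193 (NSAID use 50%). In a further version with those covariates added, the bias factor moved by at most 0.005. The direction did not change.

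The objection does not remove the point. Neither the earlier evaluation nor the planned description corrects the printed code lists or shows balance on the Table 6 renal codes.

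**Conclusion.** The concern holds. The valvular row is wrong as written, given that any listed code sets the flag and that I48 is recorded in the look-back for nearly all patients. No bias figure is claimed for it. The renal definition is incomplete. Under the assumed inputs the hazard ratio is multiplied by 0.967–0.987 (RR 1.5) or 0.939–0.975 (RR 2.0) with perfect coding, and by 0.956–0.984 or 0.918–0.969 at 50% sensitivity. In every case this favours dabigatran.

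That is well below random error for stroke/SE, but it is systematic and partly avoidable with data already held. It should be fixed before the outcome analysis; it does not invalidate the design. Confidence is medium, because the code lists programmed in 1160.279 cannot be seen and I48 may be only a typing error in Table 4.

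**What to change.** 1. Compare the code lists programmed in 1160.279, and those behind the balance report cited in section 9.7.1, with Table 4. Settle whether that report is 1160.276 or 1160.279. If the programmed lists were already right, correct Table 4 and stop there.
2. Otherwise remove I48, and the redundant I059 and I089, from valvular disease. Enter the Table 6 renal codes together with N28 as a separate yes/no kidney covariate. Refit the score and re-match.
3. Before the outcome analysis, report standardised differences for I358/I38 and for the Table 6 renal flag.
4. Add to section 9.9 that the codes capture only part of renal disease, so some renal confounding will remain.

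The cost is code-list edits, one re-run of the score and matching, and one balance table. Matched numbers may shift slightly from 4,421/4,427 per group (by under 0.1% to about 1.2% in simulation). The work should precede the analysis, which section 6 dates 18–21 July 2017 and the Abstract 1–7 July. The gain is limited to coded renal disease.
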